Date Initially Completed: 3/2/2016

or Date Updated: 06/16/2017

IRB # (if known): 4831

Protocol Title:

CAN RIVAROXABAN OR APIXABAN LEAD TO ANTICOAGULATION-RELATED NEPHROPATHY?

Protocol Version/ Date:

06/16/2017

Sponsor:

Albert Einstein Society

Investigator:

[name]

Email: [contact]

Please carefully review and complete each section of this form. If your study already has a separate protocol (e.g. developed by a sponsor or submitted as part of a grant application), you have the option to reference the section and page numbers of that protocol where appropriate in this form. PLEASE NOTE: many of the questions below are looking specifically for what will be happening locally to protect participants. This information is generally not found in a protocol written for multiple sites.

NOTE: Depending on the nature of your research, certain sections below may not be applicable. Indicate "N/A" as appropriate. You must provide a response for each section. DO NOT DELETE SECTIONS OR LEAVE SECTIONS BLANK.

Keep an electronic copy of this form. You will need to modify this form when making changes to the protocol.

1) Protocol Abstract (Briefly (in 250 words or less) describe the study in language understandable to a layperson. Include a brief description of the study purpose, target disease/condition if applicable, key eligibility criteria, and main study interventions):

Anticoagulation-Related Nephropathy (ARN) is a side effect of treatment with blood thinners which leads to kidney dysfunction. ARN is diagnosed when there is a decline in kidney function after starting the blood thinner and other possible causes of this decline have been excluded. ARN has mainly been studied in relation to the common blood thinner - warfarin, where the prevalence is variable but can be as high as 37% (approximately 1 in 3) in the patients at highest risk. The risk factors that make this side effect more likely include the presence of pre-existing kidney disease, high blood pressure, older age and diabetes mellitus. Studies have shown that the occurrence of ARN can lead to an accelerated progression of pre-existing kidney disease and a 65% increase in the risk of death (mortality).

The non-vitamin K oral anticoagulants (NOACs) are a new group of drugs which have been recently approved for use as blood thinners. They have a faster onset of action compared to warfarin and unlike warfarin, they do not need frequent monitoring. Apixaban and Rivaroxaban both have a similar mechanism of action. They inhibit Factor 10 which a clotting factor. They are the most commonly prescribed NOACs at Einstein Medical Center Philadelphia. We intend to serially monitor the kidney function by measuring the serum creatinine and urinalysis of 40 high risk patients who are recently started on either apixaban or rivaroxaban over a six month period. This will enable us to discover what proportion of patients actually develop ARN after starting a NOAC.

2) Project Objectives and Hypotheses:

Determine the incidence of ARN in high risk patients on rivaroxaban or apixaban (Factor 10 inhibitors).

Hypothesis - the incidence of ARN with apixaban or rivaroxaban is less than the previously reported incidence of ARN in warfarin.

- Describe demographic and urinalysis-associated predictors of ARN in patients on rivaroxaban or apixaban (Factor 10 inhibitors)

3) Background/Significance of Research (*Provide the scientific or scholarly background and rationale for the research based on the existing literature (include references). Describe relevant prior experience and gaps in current knowledge. Describe any relevant preliminary data. Explain the significance of the research in terms of why it's important and how it will add to existing knowledge.*):

Anticoagulation-related nephropathy (ARN) is an understudied renal complication of anticoagulant therapy that is characterized by acute kidney injury (AKI) defined as an increase in baseline serum creatinine ≥ 0.3 mg/dL, without any alternate etiology, in the setting of a supra-therapeutic International Normalized Ratio (INR) greater than 3.0 [1-7]. ARN has mainly been studied in relation to warfarin, it usually occurs in the first two months of starting anticoagulant therapy and retrospective studies have estimated the prevalence to range from 16% to 37% [4-6]. The strongest risk factor for ARN is pre-existing chronic kidney disease (CKD); other risk factors include older age, diabetes mellitus and hypertension [1,4]. Patients with ARN have an accelerated progression of CKD and a retrospective study of more than 15,000 patients on warfarin showed a 65% increase in mortality in patients with ARN [4,6].

The non-vitamin K oral anticoagulants (NOACs) are replacing warfarin in the clinical setting for long term anticoagulation because of the advantages of faster, reliable onset of action, and unlike warfarin, they do not require dose-response monitoring [8-10].

Apixaban and Rivaroxaban both have a similar mechanism of action. They inhibit Factor 10 which a clotting factor. They are the most commonly prescribed NOACs at Einstein Medical Center Philadelphia. A few animal models and case reports have shown that these NOACs (particularly dabigatran and apixaban) can lead to deterioration of kidney function, but there is limited epidemiologic data on ARN in NOACs and the incidence of ARN in NOACs is unknown [11-14]. A proposed guideline to diagnose ARN recommends that serum creatinine and urinalysis be checked monthly in the first few months of anticoagulation [1]. Clinical trials that compared warfarin to NOACs specifically studied stroke risk and bleeding outcomes and did not document the incidence of ARN because they did not make these regular creatinine and urinalysis measurements in the first few months of anticoagulation [15-20]. Our study intends to make these necessary measurements in a selected group of high risk patients started on rivaroxaban or apixaban and hence determine the incidence of ARN in this group.

This study will be the first epidemiological study using a prospective design to measure the incidence of ARN in a population receiving NOACs. Given the high morbidity and mortality associated with ARN, the findings will enhance patient safety, enabling patients and health providers to make informed decisions with their patients regarding the choice of anticoagulants. It will also establish baseline data that will serve as foundation for future studies.

SIGNIFICANCE

Anticoagulant-related nephropathy (ARN) is a relatively new and underdiagnosed complication of anticoagulant therapy with the potential to accelerate chronic kidney disease and lead to increased mortality [4,6]. Brodsky, et al, performed a retrospective study of more than 15,000 subjects and showed that the 5-year Kaplan-Meier survival rate was significantly lower in the ARN cohort compared to the patients without ARN with a 65% increased risk of mortality [4]. This dramatic increase in mortality that is attributable to an episode of ARN in a patient taking an anticoagulant is the reason why this study is very significant.

The clinical trials that compared the NOACs to warfarin did not specifically study ARN and did not repeat creatinine and urinalysis testing in the first two to three months of therapy to establish possible ARN diagnosis [15-20]. In most of these studies, only baseline creatinine and creatinine levels 6 to 12 months later were analyzed, hence it is possible that ARN was under-diagnosed as most cases of ARN are detected in the first eight weeks of therapy. Our study aims to accurately capture ARN cases by making these measurements monthly in the first three months of starting the anticoagulant.

This study is pivotal because it will for the first time, define the incidence of ARN in patients on rivaroxaban or apixaban therapy. If we find that ARN incidence in patients started on rivaroxaban or apixaban is less than that seen with warfarin, this can help support evidence that this NOAC is safer for the kidneys compared to warfarin and this data can enable us make evidence based decisions regarding the continued use of the medication to help our patients. If on the other hand we find that the medication leads to ARN, then we will be contributing important post-marketing surveillance data that can also help us make safety decisions about the use of the medication in the future.

INNOVATION

Previous studies on ARN have utilized retrospective study designs which have many epidemiological pitfalls including the cause versus effect bias and the inability to ascertain relative risk [1]. Our study is unique because we intend to utilize a prospective epidemiological design to study this renal complication, a first in the study of ARN. This is important because ARN is a diagnosis of exclusion and hence a prospective study is able to more accurately define cases of the condition compared to the assumptions that are made in retrospective studies where further work up cannot be done in retrospect.

This will be the first epidemiological study focused on ARN in a NOAC. Even though NOACs are new, they are becoming ubiquitous and a mainstay in clinical practice and not just an alternative to warfarin. For example, the recent CHEST guidelines recommend them as first line therapy in the treatment of venous thromboembolism [8]. Hence it will be important to clearly delineate their effects on the kidneys.

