Screening will be also be carried out by a query on the electronic medical record with a confidential report generated weekly by the Einstein's AECIS which will contain all rivaroxaban and apixaban prescriptions ordered by electronic scripts. Investigators and co-investigators will review the medical records of patients on the list to determine if they meet the inclusion criteria for the study.

Identified patients will be given a written description about the study and [name] (principal investigator) will be notified. All identified patients will have their medical records/chart reviewed by [name] to determine eligibility for the study. If appropriate, he will then contact them by phone and arrange a meeting to discuss the study protocol, answer any questions and complete the consent process

- ii. Describe the criteria that define who will be included or excluded in your final study sample:

Inclusion Criteria

- Age \geq 60 years
- GFR \leq 90 ml/L based on creatinine clearance
- Participant has been initiated on long term anticoagulation with rivaroxaban or apixaban for atrial fibrillation within four weeks of recruitment
- Participant is willing to comply with all aspects of the protocol, including adherence to medical therapy and follow-up visit
- Participant is willing to give written informed consent

Exclusion Criteria

- History of blood dyscrasias or active bleeding,
- History of hematuria
- Patients on dialysis

c. Study Timelines:

- i. Duration of an individual subject's participation in the study: 6 months
- ii. Time period anticipated to enroll all study subjects or to complete chart review: 4 months
- iii. Estimated overall study duration (*i.e. from initiation to completion of primary analyses*): 12 months

d. Study Endpoints:

- i. Describe the primary and secondary study endpoints (*i.e. the outcome(s) that the study is designed to evaluate*):

Primary endpoint - Incidence of ARN is the primary outcome of this study and this is based on a documentation of AKI (defined as an increase in baseline serum creatinine \geq 0.3 mg/dL), in the absence of any other obvious etiology for the AKI identified after a standard clinical evaluation and work up by the patient's primary care physician, cardiologist or nephrologist. This incidence will be expressed as a percentage.

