Secondary endpoint - Urinalysis measurements (particularly hematuria and proteinuria) will be analyzed for correlation with the incidence of ARN. Demographic variables including age and race will be analyzed in contingency tables using Fisher's exact test to ascertain if they are significant for the primary outcome.

- ii. Describe any primary or secondary safety endpoints (*e.g. any disease or symptom that would result in the withdrawal of that subject from the study*): Subjects will be censored from the study if anticoagulation is withdrawn for any clinical reason

e. Human Research Methods:

- i. Describe and explain the study design (*e.g. randomized, double-blind, placebo-controlled clinical trial or retrospective chart review*):

This is a prospective observational study designed to determine the incidence of ARN in 40 adult patients recently initiated on rivaroxaban or apixaban at Einstein Medical Center Philadelphia.

- ii. Describe all research activities involved in this protocol, including a study visit timeline if appropriate:

Baseline demographic data, past medical history, current medication list and baseline laboratory records (taken within the last three months) will be obtained from the patient's hospital chart and the electronic medical record. Serum creatinine and urinalysis measurements will then be repeated at monthly intervals for the first three months and then at the six-month mark. These laboratory tests will be drawn at Einstein's Klein building Suite 100 by a trained phlebotomist.

If AKI, defined as an increase in baseline serum creatinine ≥ 0.3 mg/dL from baseline, is noted in any study participant, the patient and his primary care physician or cardiologist will be notified both verbally and through a detailed letter. A standard clinical evaluation and work up will then be performed by the patient's primary care physician or cardiologist as part of the patient's usual care with referral to a nephrologist if necessary. The research team will then be notified of the result of this work up.

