- i. Describe steps that will be taken to secure the data (e.g. training, authorization of access, password protection, encryption, physical controls, certificates of confidentiality and separation of identifiers and data) during storage, use and transmission: As stated above, a study participant list containing identifiable data will be password protected and stored on the Einstein system. This list will only be able to be accessed by members of the research team. All other data will be stored in a separate database with unique but unidentifiable identification numbers. At the termination of the study the initial study participant list will be deleted.
- ii. Describe the data analysis plan, including any statistical procedures and method for determining the sample size for the study:

Incidence of ARN is the primary outcome of this study and this is based on a documentation of AKI (defined as an increase in baseline serum creatinine ≥ 0.3 mg/dL), in the absence of any other obvious etiology for the AKI identified after a standard clinical evaluation and work up by the patient's primary care physician, cardiologist or nephrologist. This incidence will be expressed as a percentage.

Urinalysis measurements (particularly hematuria and proteinuria) will be analyzed for correlation with the incidence of ARN. Demographic variables including age and race will be analyzed in contingency tables using Fisher's exact test to ascertain if they are significant for the primary outcome.

There is no data at all in the literature for the incidence of ARN with rivaroxaban or apixaban and we short-listed that number (40) based on the reported incidence for warfarin (17-37%). We are selecting the patients at highest risk (elderly, CKD) for anticoagulation-related nephropathy (ARN) and we expect that the incidence we obtain will be the highest for the population we are studying.

In terms of precision, we will calculate confidence intervals of the proportional incidence using Stata (command line `cii 40 (incidence)`). If the incidence is zero, Stata calculates the 95% confidence interval based on our sample size as 0-9%. If we only find 2 cases of ARN, Stata calculates the point estimate incidence at 5% with 95% confidence interval as 0.6% - 17%, If we find 10 cases of ARN, Stata calculates the point estimate incidence as 25% with 95%

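### The hypothesis and the "safer than warfarin" inference set one cohort of 40 against a historical warfarin range with a different definition, measure and ascertainment, so a lower percentage cannot be attributed to the drug

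*Protocol*

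**What the plan says.** **Hypothesis.** Section 2 (Project Objectives and Hypotheses) first sets a descriptive objective, to determine ARN incidence in high-risk patients on either drug. It then adds: "Hypothesis - the incidence of ARN with apixaban or rivaroxaban is less than the previously reported incidence of ARN in warfarin".

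**Design.** Under Human Research Methods: "This is a prospective observational study designed to determine the incidence of ARN in 40 adult patients". No warfarin patients are enrolled.

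**Intended use of the result.** The Significance part of section 3 says that if the incidence found "is less than that seen with warfarin, this can help support evidence that this NOAC is safer for the kidneys compared to warfarin".

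**Warfarin figure.** Section 3 says "retrospective studies have estimated the prevalence to range from 16% to 37% [4-6" (references 4 to 6). The sample-size text under Data Management says the number 40 was chosen "based on the reported incidence for warfarin (17-37" per cent). The same section 3 paragraph defines ARN as a creatinine rise of at least 0.3 mg/dL with no alternate cause, "in the setting of a supra-therapeutic International Normalized Ratio (INR) greater than 3.0".

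**Study endpoint.** The creatinine threshold is the same, and cases count "in the absence of any other obvious etiology for the AKI identified after a standard clinical evaluation and work up". There is no INR or equivalent condition. Creatinine is tested at months 1, 2, 3 and 6. Under Withdrawal of Subjects, patients whose anticoagulation is withdrawn for a clinical reason are censored and all their data are removed.

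**The concern.** A single-cohort percentage says something about a drug relative to warfarin only if the warfarin percentage was obtained in a comparable way. The protocol's own text shows that it was not. The Innovation part of section 3 says a prospective study defines cases more accurately "compared to the assumptions that are made in retrospective studies where further work up cannot be done in retrospect". It also lists among the weaknesses of retrospective ARN studies that they cannot yield a relative risk. The Significance part nevertheless plans an inference about relative renal safety that rests on those studies.

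At stake is the study's only hypothesis and a conclusion that the protocol says should inform continued use of these drugs. A lower percentage could arise from the definition, the case-finding or the analysis set, with no difference between the drugs. An analysis plan could not repair this, because the missing element is a like-for-like comparator.

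**Working it through.** **Step 1: reproduce the protocol's own figures.** Exact (Clopper-Pearson) 95% limits for x cases in n = 40 are: lower = Beta quantile 0.025 with parameters (x, 41 - x); upper = Beta quantile 0.975 with parameters (x + 1, 40 - x).

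| Cases | Protocol | Recomputed |
|---|---|---|
| 0/40 | 0-9% | 0-8.8% |
| 2/40 (5%) | 0.6-17% | 0.6-16.9% |
| 10/40 (25%) | 13-41% | 12.7-41.2% |

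The stated precision is right.

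**Step 2: set the two percentages side by side.**

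| Feature | Warfarin range | This study | Likely effect on this study's figure, relative to warfarin's |
|---|---|---|---|
| Creatinine rise | at least 0.3 mg/dL | at least 0.3 mg/dL | none |
| Other causes | excluded by definition; retrospective, so by assumption | excluded after prospective work-up | can lower it |
| INR above 3.0 | part of the stated definition | no such condition | raises it |
| Creatinine timing | not documented | months 1, 2, 3 and 6 | tends to raise it |
| Measure | prevalence (section 3); incidence (Data Management) | 6-month incidence | not documented |
| Denominator | not documented | 40 recent starters | not documented |
| Stopped anticoagulation | not documented | all data deleted | can lower it, if cases are among those who stop |

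The entries point both ways, and two cannot be signed from the document.

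**Step 3: what a lower result would require, taking the benchmark at face value.** The exact upper limit lies below:
- 16% with at most 1/40 cases (upper limit 13.2%);
- 17% with at most 2/40 (16.9%);
- 37% with at most 8/40 (35.6%).

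Results of 3 to 8 cases (3/40 = 7.5% to 8/40 = 20%) therefore clear the top of the range but not the bottom. Two cases clear 17% but not 16%, so even the two versions of the range can give different answers.

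**Step 4: can non-comparability alone produce a lower result?** Assume the drugs have the same true rate w, and this study records a fraction s of what the warfarin studies counted. The observed rate is then w × s. The chance that the upper limit falls below w is P(X ≤ c), with X ~ Binomial(40, w × s) and c = 1 for w = 16% or c = 8 for w = 37%.

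| s (assumed) | w = 16%: rate recorded, probability | w = 37%: rate recorded, probability |
|---|---|---|
| 1 (like-for-like) | 16%, 0.8% | 37%, 1.7% |
| 0.75 | 12%, 4% | 27.75%, 18% |
| 0.50 | 8%, 16% | 18.5%, 68% |
| 0.25 | 4%, 52% | 9.25%, 99% |

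The document gives no value for s. If s exceeds 1, because the missing INR condition and scheduled testing dominate, the error runs the other way and a real advantage could be hidden.

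**The case against.** The strongest reply is that the study is descriptive. The first objective is estimation, the analysis is a percentage with a confidence interval, no test against warfarin is planned, and the Significance sentence is hedged. Historical figures are commonly cited as context in small cohorts, and the protocol offers no INR-type criterion for these drugs that could be carried over. This stands as a limit on scope: only the hypothesis line and one inference need attention. It does not rescue the inference, because even hedged support treats the warfarin range as a comparator.

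A second reply is that dropping the INR condition and testing on a schedule would inflate the count here, so a lower result would be conservative. On those two differences alone that is right. It fails because the prospective exclusion of other causes and the deletion of data can act in the opposite direction.

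A reader might also infer stronger points that the document does not support:
- **That the study counts any AKI.** It does not. Both definitions exclude other causes; in the definition itself, the INR clause is the difference.
- **That the warfarin figures suffer from sparse creatinine testing.** The protocol's remark on sparse testing concerns the trials comparing NOACs with warfarin, not the retrospective studies behind 16-37%.
- **That the warfarin denominator is patients with INR above 3.0.** This is not stated. If 30%, 50% or 70% of starters reached that INR (pure assumption), multiplying 16-37% by those fractions would give 4.8-11.1%, 8.0-18.5% or 11.2-25.9%. This shows sensitivity and is not evidence.
- **That 4/40 would be reported as below 16%.** The planned interval is 2.8-23.7%, which contains 16%.
- **That a claim of higher risk than warfarin is planned.** None is.

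**Conclusion.** The concern holds in this form: the hypothesis and the renal-safety inference rest on a comparison that is not like-for-like, the net direction of bias is unknown, and a lower percentage cannot be attributed to the drug. This follows from the protocol's own statements on definition, measure, ascertainment and data deletion, and needs no outside figure.

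The size can only be illustrated. Under true equality, the chance of an upper limit below the benchmark moves from 0.8% to 52% (benchmark 16%), or from 1.7% to 99% (benchmark 37%), as the assumed capture falls from complete to one quarter. The document does not show that the bias favours the study drugs, so the point is that the comparison cannot be interpreted, not that it is tilted in a known direction. The descriptive estimate and its confidence interval are not called into question here.

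**What to change.** - **Section 2.** Keep the existing objective of estimating ARN incidence. Remove the comparative hypothesis, or relabel it as exploratory context.
- **Section 3, Significance.** Replace the sentence on renal safety relative to warfarin with a statement that the published warfarin figures use a different definition and ascertainment, are shown for context only, and will not support a claim of lower renal risk than warfarin.
- **Section 3 and Data Management.** Reconcile the two versions of the warfarin range (16-37% prevalence, 17-37% incidence) wherever it stays as background.

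The sample size, visits, laboratory tests and exact 95% confidence interval need no change for this. The cost is a wording amendment and a more modest stated conclusion. If the comparison itself is wanted, it would need a concurrent warfarin group assessed with the same definition and schedule, which is a different and larger study.
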